3.2 Study Endpoints

3.2.1 Primary Endpoints:

The primary endpoint is the per-subject investigator report of imaging guidance adequacy to complete the procedure (Y/N).

3.2.2 Secondary Endpoints:

The secondary endpoints are the total number of surveys reflecting the investigator opinion of procedures performed and the image data collected.

4. STUDY DESIGN

4.1 Summary of Study Design

This is a pre-market, Clinical, open label, prospective, non-randomized research study conducted at one (1) site in Canada.

4.2 Study Population

The study population will be adults undergoing vascular, gastrointestinal (GI), urology or pain management procedures for which use of the OEC Elite system in the vascular configuration would be prescribed. This population is expected to be representative of the general population that would require mobile fluoroscopic imaging with C-arm devices, such as OEC Elite. Pediatric patients (i.e. patients younger than 18 years old) will not be enrolled in this study.

4.3 Number Subjects/Cases

Up to 40 subjects may be enrolled the site. Enrollment may be discontinued at any time prior to reaching 40 subjects at the discretion of the sponsor.

4.4 Protection of Vulnerable Subjects

Vulnerable subjects are individuals whose willingness to volunteer in a clinical investigation could be unduly influenced by the expectation, whether justified or not, of benefits associated with participation or of retaliatory response from senior members of a hierarchy in case of refusal to participate.

The Sponsor shall avoid improper influence on, or inducement of, the subject, monitor, any investigator(s), or other parties participating in, or contributing to, the clinical investigation.

All investigators shall avoid improper influence on, or inducement of, the subject, Sponsor, monitor, other investigator(s), or other parties participating in, or contributing to, the clinical investigation.

This study does not examine any groups of subjects who are vulnerable subjects in the country in which the study is being conducted.

4.5 Eligibility Criteria

4.5.1 Inclusion Criteria

Subjects who meet all the following inclusion criteria may be included:

- 1) Male or female between the ages of 18 and 85 years (≥18 and ≤85 years old);
- 2) Clinical indication for procedures including vascular, gastrointestinal (GI), urology or pain management for which mobile fluoroscopy has been prescribed for image guidance;
- 3) Able and willing to comply with study procedures; and
- 4) Able and willing to provide written informed consent to participate.

4.5.2 Exclusion Criteria

Subjects who meet any of the following exclusion criteria will be excluded:

- 1) Pregnant or suspected to be pregnant based on the opinion of and as documented by a medically qualified physician investigator;
- 2) Expected to be at increased risk due to study participation (e.g. due to allergies, sensitivities), in the medical opinion of an investigator; or
- Previously participated in this study, or enrolled in another active GEHC study or other research study that could be expected to interfere with participation in study procedures, in the opinion of the investigator.

4.6 Recruiting and Screening

Subjects will be recruited for potential enrollment at the site from an adult population scheduled for a clinical procedure with mobile fluoroscopy. Subjects will be screened for enrollment against the inclusion and exclusion criteria, and enrollment determinations will be made by the site investigator. Recruitment, screening, and enrollment will be conducted per the standard procedures of the investigational site. All participation will be voluntary.

Following recruitment, a subject will be considered enrolled (the point of enrollment) once he/she signs and dates the informed consent form (ICF). Once enrolled, the subject will be assigned a unique subject number, which will not contain information that could identify him/her (e.g. subject name or date of birth). The unique subject number will be used to label case report form (CRF) data for the subject throughout his/her participation in the study.

4.7 Criteria for Withdrawal/Discontinuation

A subject may withdraw from study participation at any time, for any reason. The investigator may withdraw a subject at any time, for any reason. The reasons for withdrawal and discontinuation for any subject shall be recorded and reported to the Sponsor. The EC should be notified per their notification of subject withdrawal policy.

If a subject withdraws or is withdrawn, all efforts will be made to complete and report study data up to the time of withdrawal. A complete final evaluation at the time of the subject's withdrawal shall be made and recorded on a CRF. If the reason for withdrawal is related to an adverse event (AE) or serious adverse event (SAE), monitoring of the subject will continue until the outcome is evident.

Any data collected for the subject, up until the time of withdrawal or discontinuation, may still be included in the study results and provided to the Sponsor, unless the subject requests that their data not be used. The site shall document all requests by subjects regarding their data use.

5. STUDY PROCEDURES

5.1 Subject Preparation

Study staff will confirm that each subject is eligible and willing to comply with applicable site requirements prior to starting study procedures. No preparation beyond that required by the investigational site is required before procedures.

5.2 Description of Study Procedures

Each subject will undergo his/her clinically indicated vascular, gastrointestinal (GI), urology and pain management procedure with fluoroscopic imaging conducted using the investigational OEC Elite device. Prescribed treatments (e.g. contrasts, anesthesia) will be administered according to the standard of care.

5.3 Follow-up

No follow-up will be conducted as part of this study. Subjects will be followed for AEs from the time they enter the procedural room containing the investigational device until the study procedure ends and they exit the procedural room.

5.4 Malfunction/Error Handling

The site should report the occurrence and resolution of any procedures terminated due to non-recoverable malfunctions (i.e. malfunctions or errors with OEC Elite that prevent image collection and are not able to be immediately resolved by the device operator). The site should also report recoverable errors (i.e. issues with the device that do not prevent image collection and are able to be resolved immediately by the device operator) and operator errors. The occurrence of any recoverable error, operator error, or non-recoverable malfunction will be reported on the subject's CRF.

In uncommon cases, the research procedures using the investigational device may need to be terminated unexpectedly. If the investigator suspects that a subject would be at increased risk, or that the subject's clinical procedure will not be able to be completed using the investigational device in this study, the investigator may terminate the procedure at any time and for any reason. In some cases, it may not be feasible to end a procedure; in which case, equivalent, site-provided commercial fluoroscopy equipment (such as the predicate device or equivalent) may be used. The site will ensure that access to alternative commercial fluoroscopy equipment is maintained during all procedures. All patient care and management

decisions for terminated procedures will be made outside of this study according to the sites' standard clinical practices and the subject's regular physician's or investigator's medical judgment.

6. STUDY DATA COLLECTION AND ASSESSMENTS

6.1 Operating Physicians

At the completion of a procedure, the physician (e.g. interventional specialist or surgeon) conducting the procedure will provide feedback on the capability of the system by completing a User Survey. Survey data will be recorded on case report forms (CRFs).

7. QUALIFICATION AND TRAINING PLAN

7.1 Staff Qualifications

All members of the study staff participating in the conduct of the Clinical investigation shall be qualified by education, training, and/or experience to perform their tasks. Qualifications shall be documented appropriately, as per ISO 14155:2011.

7.2 Training Plan for the Protocol and Research Device/Product

Before starting the study, the study staff will be trained on the clinical investigation requirements set forth in this study protocol, including completion of Informed Consent Forms (ICFs), CRFs, and other study documentation. Training will also be provided to ensure appropriate storage and handling of data, and all study staff will be required to be trained on Good Clinical Practice (GCP) guidelines per ISO 14155: 2011.

A record of all formal training will be stored in the Site Regulatory Binder and provided to the Sponsor for inclusion in the Sponsor's CHF. Documentation of training will include:

- Title of Training
- Training objectives
- Training logistics (trainer and training methods)
- Documentation of trainees
- Training content (e.g. device operation, protocol review and CRF completion)

Study staff directly operating or maintaining the research device will be trained based on device operation and safety. A copy of the device operator manual will be provided to the site along with Sponsor-provided training.

The PI will be ultimately responsible for execution of this study, in accordance with the protocol, and for device use in this study by members of the study staff.

7.3 Case Report Form

The study procedure CRF will report the following:

- Basic demographic
- Type of procedure or technique being performed
- Anatomical region being imaged
- Contrast information

- User Evaluation Survey
- Guidance Adequacy

8. SAFETY

8.1 Anticipated Adverse Events

The study design is not expected to pose additional risk to patients above that required by routine diagnostic, surgical, or interventional procedures that are clinically indicated for the patient and related to use of the OEC Elite.

All subjects included in this study will require imaging during a diagnostic exam or surgery per their clinically indicated procedure. Intraoperative imaging with OEC Elite and similar commercial mobile C-arm devices produce ionizing radiation at levels generally considered safe, but in extremely rare cases, may pose risks of deterministic tissue effects (e.g. skin reddening, cataracts, and hair loss) and very small increases in lifetime cancer risk. These side effects would be risks whether or not patients participate in this study, and they are extremely rare when a mobile C-arm is used for procedures similar to the proposed study procedures. These risks generally occur only in patients exposed to excessive amounts of x-ray radiation in a short time or excessive amounts over a long period of time concentrated to a single region. These events are unusual for mobile C-arms.

Subjects may also require prescribed medications, such as contrast ("dye"), anesthesia, and other medicines that are not expected to change as a result from participation in this study. These medications have widely recognized side effects that include allergic reactions, itching, swelling, burning, bleeding, mental confusion, lung infection, stroke, heart attack, and other potentially serious metabolic complications. Patients would be at risk for these side effects whether or not they participate in this study. Patients will receive consultation on possible benefits and risks specific to their recommended procedures according to the standard of care outside of this study, and the procedures for this study will not influence these discussions.

Patient participation in this study is not expected to increase risks for side effects from imaging, contrast, anesthesia, or other medication administration or to negatively impact the results of the procedure compared to equivalent procedures performed outside of this study, using commercially available devices.

There are potential risks to subjects participating in this study that are associated with unexpected device issues or procedural complications. These risks include:

- Longer duration of patient procedures, which are expected to be minimal (accounting for time to transfer patient to alternative, commercial device and/or mitigate any other procedural or device issues) and are not expected to significantly increase the total duration of the procedure.
- Additional imaging, which could involve using an alternative, commercial system available at the site.
- Extension or interruption of regular medical care or medication administration, including prolongation; re-administration of medicines, including contrast, anesthesia, and other medicinal agents; or delay of ending anesthesia or other medications.

These events are expected to be rare, but the risks for side effects normally related to surgery, imaging, contrast, anesthesia, or other medication administration may be increased for affected patients. To minimize the impact of these risks, alternative, commercially available mobile fluoroscopy systems

available at the sites will be placed in an accessible location during all procedures that use investigational devices.

There is always a chance of unexpected risks. Throughout the study, the Sponsor will evaluate and update safety information in study documents.

8.2 Adverse Event Definitions

Adverse Event (AE): any untoward medical occurrence, unintended disease or injury, or untoward clinical signs (including abnormal laboratory findings) in subjects, users or other persons, whether or not related to the investigational medical device [ISO 14155:2011 3.2]. This includes events related to the investigational device or the comparator and to the procedures involved. For users or other persons, this is restricted to events related to the investigational medical device.

Serious Adverse Event (SAE): an adverse event that led to death; led to a serious deterioration in the health of the subject, that either resulted in a life-threatening illness or injury, a permanent impairment of a body structure or a body function, or in-patient or prolonged hospitalization, or medical or surgical intervention to prevent life-threatening illness or injury or permanent impairment to body structure or a body function; or led to fetal distress, fetal death or a congenital abnormality or birth defect. Planned hospitalization for a pre-existing condition, or a procedure required by the protocol without serious deterioration in health, is not considered a SAE [ISO 14155:2011 3.37].

Adverse Device Effect (ADE): an adverse event related to the use of an investigational medical device [ISO 14155:2011 3.1]. This includes any adverse events resulting from insufficient or inadequate instructions for use, deployment, implantation, installation, or operation, or any malfunction of the investigational medical device. This includes any event that is a result of a user error or intentional misuse of the investigational device [ISO 14155:2011 3.4].

Serious Adverse Device Effect (SADE): an adverse device effect that has resulted in any of the consequences characteristic of a serious adverse event [ISO 14155:2011 3.36].

Device deficiency: an inadequacy of a medical device with respect to its identity, quality, durability, reliability, safety, or performance, such as malfunctions, use errors, and inadequate labelling [ISO 14155:2011 3.15].

Unanticipated serious adverse device effect (USADE): a serious adverse device effect, which by its nature, incidence, severity, or outcome has not been identified in the current version of the risk analysis report [ISO 14155:2011 3.42]. In the United States, any serious adverse effect on health or safety or any life-threatening problem or death caused by, or associated with, a device, if that effect, problem, or death was not previously identified in nature, severity, or degree of incidence in the study documents, will be reported in accordance with 21 CFR §812.3 and applicable laws and regulations.

8.3 Documentation of Safety Events

All adverse events (AE), including all serious adverse events (SAE), are required to be collected, investigated, and documented during the study reporting period, as defined in the study procedure set forth in this protocol. Documentation will include:

- Description of Event
- Date of onset and resolution
- Severity (mild, moderate, or severe)
 - Mild: Symptom(s) barely noticeable to the subject or does not make the subject uncomfortable. The AE does not influence performance or functioning. Prescription drugs are not ordinarily needed for relief of symptom(s).

- Moderate: Symptom(s) of a sufficient severity to make the subject uncomfortable.
 Performance of daily activities is influenced. Treatment of symptom(s) may be needed.
- Severe: Symptom(s) of a sufficient severity to cause the subject severe discomfort. Treatment for symptom(s) may be given.
- Serious (yes/no)
- Causal relationship to investigational medical device? (not related, possibly related, or related)
 - Not related: The adverse event is reasonably expected to be related to (or caused by) a
 concurrent illness, effect of another device/drug or other cause, and is unlikely related to
 the investigational product.
 - Possibly related: The adverse event is reasonably expected to be related to the investigational product, and an alternative etiology is equally or less likely compared to the potential relationship to investigational product.
 - Related: There is a strong relationship to investigational product or recurs on rechallenge, and another etiology is unlikely or there is no other reasonable medical explanation for the event.
- Treatment given and/or action taken (procedure stopped, withdrawn from study, or no action)
- Anticipated (yes/no)

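### The AE severity scale in 8.3 rests mainly on felt discomfort and daily activities, so events seen only as signs, or under anaesthesia or sedation, cannot be graded reliably and may be under-graded

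*Combined protocol and SAP*

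**What the plan says.** Section 8.3 lists severity among the items to be documented for every adverse event and defines three grades.

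- **Mild** has three sentences: "Mild: Symptom(s) barely noticeable to the subject or does not make the subject uncomfortable"; "The AE does not influence performance or functioning"; and "Prescription drugs are not ordinarily needed for relief of symptom(s").
- **Moderate** begins "Moderate: Symptom(s) of a sufficient severity to make the subject uncomfortable", continues "Performance of daily activities is influenced", and adds that treatment of symptoms might be required.
- **Severe** calls for severe discomfort and adds that treatment might be given.

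Three other sections decide which events the scale will meet. Section 8.2 defines an adverse event to include "untoward clinical signs (including abnormal laboratory findings"). Section 5.3 says "Subjects will be followed for AEs from the time they enter the procedural room containing the investigational device until the study procedure ends" and they leave the room. Section 5.2 says "Prescribed treatments (e.g. contrasts, anesthesia) will be administered according to the standard of care", and 8.1 names delayed ending or repeat administration of anaesthesia among the risks of a device problem.

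Section 8.3 also requires, separately from severity, a description, dates, a serious yes/no flag, causality, whether the event was anticipated, and the treatment or action taken, with stopping the procedure as one of the options.

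**The concern.** The scale suits a conscious, ambulatory subject who can say how bad a symptom feels and whether it disturbs ordinary life. Here the routine observation period is the procedure itself. A subject under general anaesthesia or deep sedation reports no discomfort, and nobody in a procedure room is carrying out daily activities. An event found on a monitor or on the image, rather than reported by the subject, has no obvious place on the scale.

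This is a pre-market device study (4.1). For an event that is not serious, severity is the only graded description of how bad it was. If two investigators can grade the same event differently, or leave it ungraded, and both comply with 8.3, the field carries little information. If the literal wording pulls such events toward Mild, the field also errs in the favourable direction.

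**Working it through.** No arithmetic applies, and the plan states no figure to reproduce. The check sets the definitions side by side and then runs example events through them.

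| Criterion | Mild | Moderate | Severe |
|---|---|---|---|
| Discomfort | Barely noticed or none | Uncomfortable | Severely uncomfortable |
| Functioning | No effect on performance or functioning | Daily activities affected | Not mentioned |
| Treatment | Prescription drugs not usually needed | Possibly needed | Possibly given |
| Clinical signs | Not mentioned | Not mentioned | Not mentioned |
| Effect on the procedure | Not mentioned | Not mentioned | Not mentioned |

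**Step 1: what separates Moderate from Severe.** The treatment row sets no threshold, because treatment is permissive in both. The functioning row is silent for Severe. Only the degree of discomfort is left.

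**Step 2: coverage.** The AE definition in 8.2 covers signs; the grades in 8.3 speak of symptoms. The scale is narrower than the definition it serves.

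**Step 3: a non-serious fall in blood pressure under general anaesthesia, treated with a drug, procedure completed.** This is a hypothetical example.

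- Mild, first sentence: met, since the subject feels nothing.
- Mild, second sentence: unclear. It is not met if functioning includes physiological function, and cannot be assessed if it means what the subject can do.
- Mild, third sentence: not met if any prescription drug counts. A strictly literal reader could say that it concerns relief of symptoms and that the drug treated a sign.
- Moderate: the discomfort criterion is not met and daily activities cannot be observed.
- Severe: the discomfort criterion is not met.

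The literal reader arrives at Mild. A broader reader finds that no grade fits. An investigator using clinical judgement might enter Moderate. All three can claim to have followed 8.3.

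**Step 4: the same event, but the procedure is stopped because of it and it still does not meet the SAE criteria.** Nothing in Step 3 changes, because no grade refers to the procedure. The wording does not distinguish the two events.

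**Step 5: an awake subject.** The discomfort criterion works. The daily-activities criterion still cannot be observed within the 5.3 window, although section 4.7 extends monitoring when a subject is withdrawn because of an adverse event.

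**Step 6: what depends on the grade.** Seriousness is defined in 8.2 by outcome and by intervention. The 72-hour reporting in 8.4 turns on seriousness and on device issues. The treatment-and-action field in 8.3 is completed independently. None of these uses the severity grade.

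**The case against.** The strongest reply is that the scale has more to it than discomfort. Mild also requires no influence on performance or functioning and no ordinary need for prescription drugs, and every grade says something about treatment. A reader might infer from the first sentence alone that a major event under anaesthesia meets the definition of Mild. The full text does not support that: an event that impairs functioning or needs a prescription drug fails, or at least strains, the second or third sentence. What the text shows is an indeterminate grade that may come out too low; systematic downgrading is not shown. This part of the reply stands.

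It also stands that grave events are caught elsewhere. The SAE definition is outcome-based and includes intervention to prevent life-threatening harm, and reporting to the sponsor does not wait on the severity grade. An event that was treated, or that stopped the procedure, is recorded as such in the treatment-and-action field. A reader might infer that the safety record as a whole would look too benign. The documents do not support this either: they describe no severity listing, no endpoint in 3.2 uses the grade, and 10.3 plans no statistical analysis.

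Finally, anaesthesia may be local, pain management procedures are included, and depth is not stated, so some subjects will be able to report discomfort.

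What the reply does not answer is the mismatch itself. The other fields record what was done, but do not tell an investigator which grade to enter. The treatment wording cannot help, because it sets no threshold between Moderate and Severe.

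**Conclusion.** The point holds in limited form. The scale relies mainly on perceived discomfort and daily activities, has no criterion based on signs or intervention, and separates Moderate from Severe only by degree of discomfort. Events detected as signs, and events in subjects who are anaesthetised or sedated enough not to report discomfort, cannot be graded reliably and may be under-graded.

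The consequence is confined to the severity field for non-serious adverse events. SAE classification, expedited reporting and the primary endpoint are untouched.

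The number of affected events cannot be derived. A reader might be tempted to apply an assumed anaesthesia share to the enrolment ceiling of 40: 25% would give 0.25 × 40 = 10 subjects and 75% would give 0.75 × 40 = 30. That range counts subjects, not events. The share has no basis in the documents, and 4.3 lets the sponsor stop below 40. It should not be used as a measure of size.

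The conclusion assumes that at least some procedures involve anaesthesia or sedation deep enough to prevent reporting of discomfort, or that some events appear only as signs. Sections 5.2, 8.1 and 8.2 make both plausible; none gives a frequency.

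**What to change.** In 8.3, and in the guidance for completing the AE form, add a second set of anchors for events detected as signs or occurring under anaesthesia or sedation, tied to the existing treatment-and-action field:

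- **Mild:** transient, with no intervention.
- **Moderate:** an intervention was given and the procedure continued.
- **Severe:** an urgent intervention was given, or the procedure was interrupted or ended because of the event.

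Keep the symptom wording for awake subjects, and state that the higher grade applies where the two sets differ. These are recording definitions, applied after the fact; they do not direct patient management.

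The cost is a few lines of text, with no added visits, staff or subjects. Most of the information is already required by 8.3. Urgency, and an interruption short of stopping, are not named options there and would have to come from the event description. There are two drawbacks: some events will carry a higher, less favourable grade, and the grade will partly overlap with the treatment-and-action field.
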